4.1. Overall Design

This is a randomized, double-blind, placebo-controlled, parallel-group, 2-arm, multicenter trial.

- Subjects hospitalized due to ongoing COVID-19 will be enrolled.
- The trial consists of 3 consecutive periods: a screening period of up to 48 hours, a 2-week IMP treatment period and a follow-up period of up to 7 weeks. Daily visits are required until discharge. Discharged subjects should return to the clinic for the Day 15 visit. Days 8, 22, 29 and 60 visits will be conducted as phone or video visits for all discharged subjects.
- The trial duration for an individual subject will not exceed 9 weeks.
- The trial will enroll a total of maximum 300 randomized subjects, 150 per arm (C21 100 mg b.i.d. or placebo for 14 days) according to a 1:1 randomization.
- Blinding will be performed with a matching placebo.
- Randomization occurs at visit 2 and will be stratified by:
 - Disease severity (based on the ordinal scale score at Day 1).
 - Region.
- An independent DMC will actively monitor data from the trial.

4.2. Scientific Rationale for Trial Design

The proposed clinical trial design is based on the guidance provided in the WHO COVID-19 therapeutic trial synopsis ([WHO, 2020b](#)), the FDA Guidance for Industry to support clinical development of drugs for the treatment and prevention of COVID-19 ([FDA, 2020a](#)), investigator and authority guidance.

The trial will enroll hospitalized subjects with a confirmed SARS-CoV-2 infection and on supplemental oxygen but not requiring mechanical invasive ventilation. There is a high unmet need for an efficacious treatment of COVID-19 in this population to halt respiratory failure and ultimately reduce mortality.

The primary endpoint is all-cause mortality up to Day 60. This endpoint is considered clinically relevant in the population studied and the timepoint of evaluation will ensure capturing the majority of events to assess a treatment response.

The primary endpoint is supported by data from the completed Phase 2 trial (VP-C21-006), in which C21 was associated with a numerical reduction in the mortality rate (one and three deaths in the C21 and placebo group, respectively). All deaths occurred in patients with progressive respiratory insufficiency and need for mechanical ventilation. One more patient in the placebo group deteriorated and developed need for mechanical ventilation.

The 8-point ordinal scale together with an assessment of supplemental oxygen use will be used for assessment of the key secondary endpoints. The ordinal scale is considered responsive to the selected COVID-19 population with respect to the treatment and course of the illness and such

scales have been used in the majority of phase 2 and 3 COVID-19 trials to date ([Dodd et al., 2020](#)). The 8-point ordinal scale is a composite measure of clinical improvement and/or survival assessed up to 60 days post randomization.

It has been demonstrated that there is a strong association between days on oxygen during the acute phase of COVID-19 and long-term recovery ([Shah et al., 2021](#)). In the Phase 2 trial, patients on C21 had a significantly lower use of supplementary oxygen therapy at end of treatment, only 1 out of 51 subjects in the C21 group was using supplemental oxygen at Day 14.

The WHO COVID-19 therapeutic trial synopsis recommends that subjects will be treated with IMP on top of SoC in ([WHO, 2020b](#)). Guidance on SoC is provided in Appendix 4 (see Section 10.4).

The placebo group and the blinding in the trial was implemented to minimize bias. The randomization will be stratified to ensure an equal distribution of active and placebo subjects by region and disease severity.

4.3. Justification for Dose

Subjects will be treated with oral 100 mg C21 or placebo b.i.d. for 14 days.

The results of the completed phase 2 trial in COVID-19 subjects (VP-C21-006) and of the phase 1 trial in healthy subjects (VP-C21-003) indicate an acceptable safety and tolerability profile for the 100 mg b.i.d. dose. The risks of C21 in adults are considered primarily related to reversible alopecia seen at the higher dose of 200 mg b.i.d. In the phase 2 trial in COVID-19 subjects (VP-C21-006) and the phase 1 trial (VP-C21-003), the 100 mg b.i.d. dose did not cause any hair loss (Further details can be found in the IB). Alopecia is therefore not considered to present any significant safety risk to subjects in this trial.

In the phase 1 trial (VP-C21-003), 100 mg b.i.d. dosing prolonged the duration of the plasma concentration at therapeutic relevant levels. After oral administration, C21 was rapidly absorbed. On Day 8, median t_{max} was 0.33 hours after each dose post-dose, and C21 was measurable in plasma until 4-6 hours after the first and second dose. Lower doses than 100 mg b.i.d. may not provide maximal efficacy benefit.

In the completed phase 2 trial (VP-C21-006) in COVID-19 subjects, treatment with 100 mg b.i.d. for 7 days, reduced the need for extended oxygen supplementation.

The recently completed phase 2 trial (VP-C21-006) indicates that C21 can prevent hypoxic critical illness and based on the course of the disease, there is a strong rational to extend the treatment duration from 7 to 14 days. Furthermore, 27% of subjects within the C21 arm were still in need of oxygen (vs 45% on placebo) at the end of the 7 days treatment, highlighting an opportunity to treat for a longer period to gain additional benefit, with the aim of returning patients to normoxia.

There is not enough evidence to treat beyond 14 days at this stage.

Based on the above, C21 will be administered at an oral dose of 100 mg b.i.d. for 14 days in the present trial.

4.4. End of Trial Definition

End of trial is defined as the date of the last visit of the last subject in the trial.

A subject is considered to have completed the trial if he/she has completed all periods of the trial including the Day 60 visit.

5. Trial Population

The trial will enroll adult subjects hospitalized due to SARS-CoV-2 infection.

Prospective approval of protocol deviations to recruitment and enrollment criteria, also known as protocol waivers or exemptions, is not permitted.

5.1. Inclusion Criteria

Subjects are eligible to be included in the trial only if the following criteria are fulfilled:

Age

1. Age ≥ 18 years or the legal age of consent in the jurisdiction in which the trial is taking place at the time of signing the informed consent. (*Specific for India*; Age ≥ 18 at the time of signing the informed consent to ≤ 65 years.)

Type of Subject and Disease Characteristics

2. Hospitalized due to SARS-CoV-2 infection confirmed by a hospital-approved polymerase chain reaction (PCR) test, documented by either of the following:
 - a. PCR positive in sample collected <72 hours prior to randomization (Visit 2); OR
 - b. PCR positive in sample collected ≥ 72 hours and ≤ 7 days prior to randomization, documented inability to obtain a repeat sample AND progressive disease suggestive of ongoing SARS-CoV-2 infection.
3. A score of 5 or 6 on the 8-point ordinal scale:
 - a. Score 5: Hospitalized, requiring supplemental oxygen.
 - b. Score 6: Hospitalized, on non-invasive ventilation or high-flow oxygen device.

Sex and Contraceptive/Barrier Requirements

4. Contraceptive use by men and women of childbearing potential consistent with local regulations regarding the methods of contraception for those participating in clinical studies and according to Appendix 3 (see Section 10.3).

Informed Consent

5. Written informed consent, consistent with International Council for Harmonization (ICH) Good Clinical Practice (GCP) R2 and local laws, obtained before the initiation of any trial-related procedure.
6. Capable of giving signed informed consent as described in Appendix 1 (see Section 10.1.3) which includes compliance with the requirements and restrictions listed in the informed consent form (ICF) and in this protocol.

Country specific

7. Specific for India: For subjects with an ordinal scale score of 5, moderate to severe COVID-19 disease confirmed by at an $\text{SpO}_2 \leq 93\%$ or a respiratory rate $\geq 24/\text{min}$ on room air. Note: If a subject is on supplemental oxygen with $\text{SpO}_2 > 93\%$ and respiratory rate $< 24/\text{min}$, but desaturation to $\leq 93\%$ or increase of respiratory rate to $\geq 24/\text{min}$ on lower supplemental oxygen or room air is documented during screening, the inclusion criterion is considered to be met.

5.2. Exclusion Criteria

Subjects are excluded from the trial if any of the following criteria apply:

Medical Conditions

1. Concurrent serious medical condition which in the opinion of the investigator constitutes a risk or a contraindication for the participation in the trial or that could interfere with the trial objectives, conduct or evaluation.
2. Known, active tuberculosis, active hepatitis B, C, or human immunodeficiency virus (HIV) infection (i.e., HIV with a CD4 count <500 cells/mm³).
3. Moderate or severe impairment of hepatic function (e.g., Child-Pugh class B or C where alterations in the score components are not due to another underlying disease (see Section 8.4.5)).
4. Severe renal impairment (i.e., estimated glomerular filtration rate (eGFR) ≤ 30 ml/min/1.73 m²).
5. COVID-19 symptom onset >21 days prior to screening (Visit 1).
6. Hospitalized due to COVID-19 for >72 hours at screening (Visit 1).
7. Invasive mechanical ventilation or ECMO within 72 hours of screening (Visit 1).
8. Expected need for invasive mechanical ventilation or ECMO in <48 hours in the opinion of the investigator.
9. Moderate to severe ARDS (e.g., same-day PaO₂/FiO₂ ≤ 200 mmHg; or SpO₂/FiO₂ ≤ 232 if arterial blood gas test is not available), if on non-invasive mechanical ventilation or high-flow oxygen.
10. Pregnant or breast-feeding female subjects.

Prior/Concomitant Therapy

11. Any previous and concurrent experimental treatment for COVID-19 that is not considered local SoC.
12. Treatment with the medications listed below within 1 week prior to screening (Visit 1) or anticipated need for such medication during the participation in this trial:
 - a. Strong Cytochrome P450 (CYP) 3A4 inducers.
 - b. P-glycoprotein (P-gp) substrates with narrow therapeutic index.
 - c. High dose BCRP sensitive substrates.
 - d. Warfarin.
 - e. Sulphasalazine or rosuvastatin.

Prior/Concurrent Clinical Trial Experience

13. Current or previous participation in any other clinical trial where the subject has received a dose of IMP within 1 month or 5 half-lives of the IMP, whichever is longest, prior to screening (Visit 1).

Diagnostic Assessments

14. Positive pregnancy test (see Section 0).
15. Abnormal laboratory value at screening (Visit 1) indicating a potential risk for the subject if enrolled in the trial as evaluated by the investigator.

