9.3. Statistical Analyses

9.3.1. General Considerations

All tests will be 2-sided at a 5% significance level.

Baseline will be defined as the last non-missing assessment obtained prior to first IMP administration.

Stratification will be done based on baseline disease severity, that is the score on the ordinal scale at baseline (5 or 6), and region (North America, South and Central America, Europe, Africa, or Asia). The actual stratification will be used as factors in the statistical analysis, subjects included in wrong stratum at randomization will be moved to their correct strata belonging in the analyses. Due to small strata, the regions may be merged; details of this will be given in the SAP.

Continuous variables will be summarized using (arithmetic) means, standard deviation (SD), median, minimum, and maximum value, categorical variables will be summarized using numbers and percentages. For variables with an expected skew distribution, geometric means, and coefficient of variation (CV) will be used instead of arithmetic means and SD.

The ITT analysis set is used to analyze endpoints related to the efficacy objectives, the PP analysis set will be used for sensitivity analyses related to efficacy objectives and the safety analysis set is used to analyze the endpoints and assessments related to safety. PK data will be presented using the PK analysis set.

All data regarding subject characteristics, efficacy and safety will be listed.

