9.5. Sample Size Determination

The sample size is based on the all-cause mortality up to Day 60. For the placebo (SOC) group, the proportion of subjects dead at Day 60 is estimated to 10% ([Marconi et al., 2021](#)).

With 150 evaluable subjects per trial group, there will be an 80% power to detect a difference between C21 and placebo if the proportion of subjects dead at Day 60 in the C21 group is 2.5% (corresponding to a HR of 0.24). In this calculation, a 5% withdrawal rate has been assumed. For the actual detection limit (corresponding to 50% power), if 15 subjects die in the placebo group, significance will be seen if at most 6 subjects die in the C21 group.

This assumes using a 2-sided test at a 5% significance level. Analysis will be by intention-to-treat; thus, all randomized subjects should be accounted for in the statistical evaluation.

10. Supporting Documentation and Operational Considerations

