10.4. Appendix 4 Standard of Care for COVID-19

All subjects receiving IMP will also receive SoC for COVID-19, which may include:

- Oxygen administration to maintain oxygen saturation of 90 % to 96 %, including supplemental oxygen (low flow or high flow), non-invasive or invasive mechanical ventilation or ECMO
- Frequent clinical assessments of neurological, pulmonary, cardiac, gastrointestinal, and urinary status as required depending on clinical status
- At least daily monitoring of vital signs (heart rate, blood pressure, body temperature, respiratory rate and oxygen saturation (SpO₂))
- Telemetry monitoring to evaluate heart rhythm and rate
- Diet as tolerated to satisfy nutritional needs
- Mobilization of the subject and rotation to prone positioning of ventilated subjects
- Treatment for COVID-19 symptoms including antibiotics, cough suppressant / expectorants, anti-coagulants, analgesics, antipyretics, antiemetics and/or bronchodilators; refer also to section 6.8 regarding permitted prior or concurrent therapy
- Treatments for COVID-19 which are: Administered in accordance with approved conditions by the national health authority (*Specific for India*; Indian Council for Medical Research (ICMR) guidelines for management of COVID-19 patients ([ICMR, 2021](#))), including emergency use authorizations, conditional approvals, or article 5(3) reviews,

AND

- Approved under such conditions in the US or EU, and/or recommended in international consensus guidelines (e.g., remdesivir, dexamethasone, tocilizumab, convalescent plasma, and certain monoclonal antibodies). See section [6.8](#) regarding permitted prior or concurrent therapy.

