12.5.2.2 Primary Analysis

All-cause mortality at Day 60 will be defined as time to day of death from any cause within Day 1 to Day 60 follow-up (refer to Section 10.11). All-cause mortality will be estimated using the Kaplan-Meier methodology where subjects in this analysis without the event will be censored at Day 60 follow-up. Withdrawn subjects without the event will be censored at day of discontinuation (this assumes the censoring is non-informative).

Treatment groups will be compared using a stratified log-rank test adjusting for treatment, actual baseline disease severity and region. The p-value from the stratified log-rank will be presented. The size of the treatment effect will be estimated as a hazard ratio, obtained using a Cox proportional hazards regression model, and the Cox regression model will include a factor for randomized treatment, baseline disease severity and region. The estimated Hazard Ratio comparing C21 to Placebo will be presented together with the corresponding 95% CI (based on Wald test). A Kaplan-Meier plot of time to all-cause mortality will also be produced.

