12.5.2.4 Supplementary Analyses

Additional analyses examining the consistency of the intervention effect in the following subgroups using the ITT will be performed. A forest plot and repeat of the analysis as per Section 12.5.2 in the following subgroups will be presented:

- Age group: <65 vs ≥65 years
- Sex: female vs male
- Actual baseline disease severity (8-point ordinal scale 5 or 6 at Day 1)
- Race (American Indian or Alaska Native, Asian, Black or African American, Native Hawaiian or Other Pacific Islander, White or Other)
- Ethnicity (Hispanic or Latino, Not Hispanic or Latino)
- Region (Europe, Rest of the World)
- Presence of risk factors for severe COVID-19 (Yes, No)

The subgroup categories may be redefined prior to unblinding the study due to the following reasons:

- If the number of subjects is too small (less than 10% of the ITT population) within a subgroup then only the categories with >10% of subjects will be presented in the output.
- If other subgroups appear to be of interest (for example the medications used as SOC) they will be included in the summary.

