Appendix 3: Imputation of FiO₂ values

If the value of FiO₂ is missing when the type of low flow device and oxygen flow is given, the below values will be used as the value of FiO₂ in the analysis. For example if a subject at a visit has a low flow device type of "Open Mask" with oxygen flow of 5 L/min, for analysis purposes a value of 40(%) for FiO₂ will be used.

It should be noted that sites are permitted to enter a range of values. For example if a site states the subject is on a low flow nasal cannula with oxygen flow of 3, the site can enter a range of FiO₂ from 28 to 36. No adjustments will be made in the analysis for site entered values to align with the below literature. Sites are also permitted to enter values that are outside the values presented in the reference tables (for example nasal cannula > 15 L/min).

- **Low Flow Nasal Cannula (Simon et al., 2016)**

Oxygen Flow (L/min)	Fraction of Inspired Oxygen (%)
1	24
2	28
3	32
4	36
5	40
6-15	44

- **Low Flow Open Mask (Simon et al., 2016)**

Oxygen Flow (L/min)	Fraction of Inspired Oxygen (%)
1	24
2	28
3	32
4	36
5	40
6-7	50
8-15	60

- **Venturi Mask (Batool and Garg., 2017)**

Oxygen Flow (L/min)	Fraction of Inspired Oxygen (%)
2 (blue)	24
4 (white)	28
6 (orange)	31
8 (yellow)	35
10 (red)	40
15 (green)	60

- **Partial Rebreather Mask (Batool and Garg., 2017)**

Oxygen Flow (L/min)	Fraction of Inspired Oxygen (%)
6	60
8	70
10	80

- **Non-rebreather Mask (MEDEST, 2020)**

Oxygen Flow (L/min)	Fraction of Inspired Oxygen (%)
10-15 L/min	80-100
Both flaps removed	80-85
One flap removed	85-90
Both flaps in place	95-100

- **Small Diffuser (OxyMask) (Paul et al., 2009)**

Oxygen Flow (L/min)	Fraction of Inspired Oxygen (%)
1.5	25
2	30
2.5	37
3	42
5	58
10	74
15	80

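### The score 5 versus 6 severity factor is a coarse measure of respiratory support; adding baseline SpO2/FiO2 to the Day 15 models is a cheap gain in precision

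*Protocol*

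**What the plan says.** Protocol section 5.1 admits score 5 (hospitalized on supplemental oxygen) and score 6 (non-invasive ventilation or a high-flow device). Exclusion 9 in section 5.2 removes moderate to severe ARDS. It gives as examples a same-day PaO2/FiO2 of 200 or less, or SpO2/FiO2 of 232 or less if there is no arterial blood gas, and applies this only "if on non-invasive mechanical ventilation or high-flow oxygen".

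Disease severity is defined throughout as score 5 or 6. It is a randomization stratum and a stratum of the log-rank tests. It also enters the hazard ratio models: in SAP section 12.5.2.2, "the Cox regression model will include a factor for randomized treatment, baseline disease severity and region". The Appendix 2 logistic models, the imputation model and the ANCOVAs use it too. The subgroup list in SAP section 12.5.2.4 includes "Actual baseline disease severity (8-point ordinal scale 5 or 6 at Day 1").

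Baseline SpO2/FiO2 is a covariate in one place only, the ANCOVA of its own change to Day 15 (Protocol section 9.3.3, SAP section 12.5.4). That analysis needs a Day 15 value, so it omits anyone who died before then. The baseline summaries in SAP section 12.2 list oxygen device type but not the ratio.

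**The concern.** The score records the device in use, not how well the subject oxygenates. Because exclusion 9 screens oxygenation at one level of the factor and not at the other, some subjects in the milder stratum may have worse gas exchange than anyone admitted to the more severe stratum on the SpO2/FiO2 criterion. Protocol section 2.3.2 states that hypoxemia is independently associated with in-hospital mortality, and the primary endpoint is mortality.

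Two things are at stake. First, a prognostic baseline value that is already collected does not help precision in the models for the two Day 15 key secondary endpoints, and a chance imbalance in it would not show in the planned baseline tables. Second, a difference in effect between scores 5 and 6 could be read as a difference by severity when one level was screened for oxygenation and the other was not.

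**Working it through.** **1. The plan's own power figure.** Inputs from Protocol section 9.5: 150 per arm; in the placebo group "the proportion of subjects dead at Day 60 is estimated to 10"%; 2.5% on C21; 5% withdrawal; "there will be an 80% power to detect a difference between C21 and placebo". From section 9.3.1: "All tests will be 2-sided at a 5% significance level".
- Hazard ratio: ln(0.975)/ln(0.90) = 0.240, as stated.
- Simulated log-rank test (exponential times, 4,000 runs): 79.6% power without withdrawal and 78.7% with 5% uniform withdrawal. The 80% is reproduced to within 2 points.
- Detection limit by uncorrected chi-square: 15/150 v 6/150 gives p = 0.042, and 15/150 v 7/150 gives p = 0.076. The stated limit of 6 is reproduced.
- Expected deaths: 150 x 0.10 + 150 x 0.025 = 15 + 3.75 = 18.75.

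**2. What exclusion 9 implies for score 6.** Appendix 4 of the Protocol lists, among elements that standard of care may include, "Oxygen administration to maintain oxygen saturation of 90 % to 96"%. Where eligibility is judged by the saturation ratio, FiO2 must be below SpO2/232:
- at SpO2 90%: 90/232 = 38.8%
- at SpO2 96%: 96/232 = 41.4%

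**3. What score 5 allows.** SAP Appendix 3 assigns FiO2 when it is missing, for example "if a subject at a visit has a low flow device type of" open mask at 5 L/min, which gets 40%. Using its values as a guide, the ratio is 100 x SpO2/FiO2:

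| Device and flow | FiO2 (%) | Ratio at SpO2 90-96% |
|---|---|---|
| Cannula 1 L/min | 24 | 375-400 |
| Cannula 4 L/min | 36 | 250-267 |
| Cannula 5 L/min | 40 | 225-240 |
| Cannula 6-15 L/min | 44 | 205-218 |
| Open mask 6-7 L/min | 50 | 180-192 |
| Open mask 8-15 L/min | 60 | 150-160 |
| Non-rebreather | 80-100 | 90-120 |

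Exclusion 9 bars none of these rows at score 5. At score 6, a ratio of 232 or less would be barred if no blood gas was available.

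**4. Effect on the primary test.** The documents give no distribution of the ratio and no mortality by ratio, so this is an illustration on assumed inputs: 30% of subjects at or below 232, a 5/6 score (20% score 6) with no severity information at all, and a death hazard 3 or 5 times higher at low ratios. It used 3,000 runs with 5% withdrawal.

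| Hazard multiple | Power, stratified by score | Power, stratified by ratio class | Type I error (score / ratio class) |
|---|---|---|---|
| 3 | 78.8% | 79.5% | 4.9% / 4.8% |
| 5 | 79.7% | 80.9% | 5.5% / 5.1% |

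Monte Carlo standard errors are about 0.7 points (power) and 0.4 points (type I error). The loss is about 1 point, and type I error stays near 5%.

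**5. Effect on a Day 15 responder model.** This simulation used 2,500 trials of 300, 25% at score 6, and the Appendix 2 type of risk difference with the 5/6 factor already in the model. It then added a within-score covariate with an assumed odds ratio per SD of 1.5, 2.0 or 2.5. The variance ratios were 0.96, 0.91 and 0.87. Power rose from 74 to 75%, 70 to 74% and 67 to 73%. Other runs with the same odds ratios gave variance reductions between 2% and 16% and power gains of 2 to 7 points, with type I error near 5%.

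**The case against.** A reader might infer from exclusion 9 that the strata fail to order severity, or that the analyses leave severity unadjusted. The documents support neither.

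- **Ordering.** No SpO2/FiO2 distribution and no mortality by score is given. Most score 5 subjects could be on low flows with ratios of 250-400, and score 6 still means more support. Inversion is possible, not shown.
- **Adjustment.** The score is in nearly every efficacy model. The main exception is the Wilcoxon test for oxygen-free days, and its ANOVA sensitivity analysis includes the score. What is missing is gas exchange within a score.
- **The limit itself.** Both cut-offs are examples, and 232 applies only without a blood gas. A score 6 subject with PaO2/FiO2 above 200 and a ratio at or below 232 stays eligible. Exclusion 8 (expected invasive ventilation or ECMO within 48 hours, in the investigator's opinion) applies to both scores.
- **Bias.** Randomization protects the comparison, so only precision and interpretation are affected.
- **The simulated gain.** It measures the value of a prognostic covariate in general and does not model the asymmetry in exclusion 9. The Day 15 endpoints rank fourth and fifth in the hierarchy.
- **Practicality.** Appendix 3 fills FiO2 only for low-flow devices and gives a range for non-rebreathers. SAP section 10.18 uses the room-air reading alone when a visit has both, and at FiO2 21% the ratio exceeds 232 whenever SpO2 exceeds 0.21 x 232 = 48.7%. The existing ANCOVA drops subjects without a ratio. About 19 deaths is few for a further Cox term.

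All of these stand. They limit the claim and shape the fix. They do not remove the asymmetry in exclusion 9 or the absence of a within-score gas-exchange covariate.

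**Conclusion.** This is a cheap improvement, not an error that threatens the trial. The 5/6 factor is a coarse measure of respiratory support whose levels can overlap or invert on SpO2/FiO2, and the primary and key secondary analyses do not adjust for gas exchange within a score. The stated power and sample size are unaffected. The stratified log-rank test remains valid and, in the extreme illustration, loses about 1 point of power. The gain available in the Day 15 logistic models is roughly 2-16% in variance and 1-7 points in power. It depends on assumed odds ratios of 1.5-2.5 per SD, which the documents neither give nor contradict. The 5 versus 6 subgroup remains a legitimate display, but it shows effect by level of support.

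**What to change.** Before unblinding, leave eligibility and the stratified log-rank test as they are, and amend the SAP as follows.

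- Add baseline SpO2/FiO2, as a continuous covariate, to the Appendix 2 logistic models for the two Day 15 key secondary endpoints.
- Tabulate it by arm with the other baseline characteristics.
- Add it to the mortality Cox model only as a sensitivity analysis, given about 19 expected deaths.
- For this covariate, use the on-device reading instead of the room-air rule in section 10.18, and fix in advance a single FiO2 value where Appendix 3 gives a range.
- Fill any remaining missing baseline ratio by a simple rule, such as the screening value and then the mean within score, so that no ITT subject is dropped.
- Describe the 5/6 subgroup as baseline respiratory support when interpreting it. A subgroup at 232 or less versus above 232 is optional.

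The cost is SAP wording, some derivation and a few outputs. Saturation is already scheduled at screening and Day 1, and Protocol section 8.2.3 already requires device, flow and FiO2 with it. The downside is measurement error: FiO2 on low-flow devices is approximate, and Appendix 3 lets sites enter differing values, which will reduce the gain.
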